7.8 Storage and analysis of clinical samples

Not applicable.

7.9 End of trial

The trial will be considered complete when all participants have completed 18 months of treatment, and have completed 6 months of follow-up. The total length of the study may be up to 3 years.

8 TRIAL INTERVENTION

8.1

All participants will undergo a comprehensive Mentalisation Based Treatment (MBT) program.

This includes a weekly individual session lasting 50 minutes and a weekly group session of 75 minutes. The treatment will last for 18 months, as per the time specified in the treatment manual. The four clinicians delivering the treatment will participate in a weekly 90-minute peer supervision and receive bi-weekly group supervision of 60 minutes from an MBT expert, who is an accredited MBT supervisor. All these clinicians either have 'practitioner level status in MBT' or are in a program working towards this status.

9 ADVERSE EVENTS AND SERIOUS ADVERSE EVENTS

9.1 Definitions

Term	Definition
Adverse Event (AE)	Any untoward occurrence in a participant to whom an intervention has been administered, including occurrences which are not necessarily caused by or related to that product.
Serious Adverse Event (SAE)	 A serious adverse event is any untoward that: results in death is life-threatening requires inpatient hospitalisation or prolongation of existing hospitalisation results in persistent or significant disability/incapacity
	NOTE: The term "life-threatening" in the definition of "serious" refers to an event in which the participant was at risk of death at the time of the event; it does not refer to an event which hypothetically might have caused death if it were more severe.

9.2 Operational definitions for (S)AEs

1) Suicide

In the event that participant dies as the result of suicide, or the cause of a participant's death is suspected to be suicide, then this will be reported to the sponsor using the case report form.

The research team will report the event to the Sponsor, including the participant number, date of incident, as well as any information contained in an investigation that demonstrates any causative link between the study and the severe adverse event.

Life-threatening suicidal behaviour will be recorded throughout the study if it takes place.

9.3 Safety of intervention

There is no evidence to suggest that MBT causes serious or severe adverse events such as suicide. An RCT examining the impact that MBT has upon suicidal adults (including 168 participants) found a significant reduction in life threatening suicide attempts, serious self-harm incidents and hospitalisation (Bateman & Fonagy 2009). At baseline, all participants had engaged in self-harm, suicide attempts or had been admitted to hospital. At 8 year follow up, 75% of the follow up group had no incidents of self-harm, suicidal behaviour or hospital admission. As such, it is likely that MBT is protective against suicide and self-harm in adults.

9.4 Endpoints for the intervention

If participants end their life due to suicide which is linked to the intervention, the study will be stopped.

9.5 Recording and reporting of SAEs

Serious adverse events relating to suicide will be reported immediately to the sponsor. If a participant dies by suicide 6 months after the stud has ended, this will not be reported to the sponsor.

All SAEs occurring from the time of written informed consent until 6 months post cessation of trial treatment must be recorded on the CRF, and sent to the Sponsor **within 24 hours** of the research staff becoming aware of the event. Once all resulting queries have been resolved, the Sponsor will request the original form should also be posted to the Sponsor and a copy to be retained on site.

For each SAEs the following information will be collected:

- full details in medical terms and case description
- event duration (start and end dates, if applicable)
- action taken
- outcome
- seriousness criteria
- causality (i.e. relatedness to trial drug / investigation), in the opinion of the investigator
- whether the event would be considered anticipated.

Any change of condition or other follow-up information should be faxed to the Sponsor as soon as it is available or at least within 24 hours of the information becoming available. Events will be followed up until the event has resolved or a final outcome has been reached."

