3.3 Outcome measures/endpoints

The endpoint for the study's outcome will be at 24 months. This will include 18 months of treatment, and 6 months of follow up.

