3.7 Table of endpoints/outcomes

Objectives	Outcome Measures	Timepoint(s) of evaluation of this outcome measure (if applicable)
Primary Objective Personality Functioning Social isolation	LPFS 2.0. Social Isolation Short Form 4.0	Both questionnaires are given from day 0 till the end of data collection period at 24 months. Patients are requested to fill out these two questionnaires on a weekly basis during waiting period, treatment and follow up.
Service use Self injury and suicidal behaviour	Service use Suicidal behaviour	Data to be taken from clinical records at 0,6,12,18, and 24 months
Feasibility	Comparison of recruitment rate, drop out, and completion	Data to be taken at 0, 6, 12, 18, 24 months
Acceptability	Thematic analysis of qualitative interview	Analysis of data at 24 months
Secondary Objectives		
To evaluate	ReQoL 10	Measures provided at 6 month
quality of life (ReQol),		intervals, at 0,6,12,18, and 24 months.
patient satisfaction (Dialogue),	Dialogue	months.
and suicidality (Columbia Scale).	CSRSS (Columbia Scale)	

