7.7 Withdrawal criteria

Participants can withdraw from the trial at any time, for any reason. They may choose to withdraw from different elements of the trial including:

- Withdrawal from MBT treatment only.
- Withdrawal from data collection.
- Withdrawal from the qualitative interviews.
- Withdrawal from any analysis of data from the participant's medical records.

If the participant wishes to withdraw, then they can do so at any time. If it is made clear, their rationale for withdrawing will be recorded and stored securely, and this will be made clear in the final report of the study. Participants may be replaced if the dropout rate is such that the statistical power of the study will be negatively impacted. This will increase the length of the trial, and as such an amendment from the REC will need to be sought, if the anticipated length of the trial will exceed 3 years.

Any participants that withdraw from the trial will be asked if they would like to continue to be involved in data collection, and follow up. They can withdraw from this aspect of the study.

If there are multiple severe adverse events, the trial may be stopped, if there is a direct link between the study and the adverse event.

In the event of a participant withdrawing from the study, they will be asked if the data collected to that point can be continued to be used in the data analysis. If they withdraw consent for their data to be used, it will be destroyed. All participants that withdraw will be offered an exit interview, using the theoretical framework of acceptability. Participants can refuse this interview with no impact to their clinical care. Participants can withdraw from the study but continue to access the treatment.

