9.7 Notification of deaths

All deaths will be reported to the sponsor irrespective of whether the death is related to disease progression, the IMP, or an unrelated event". As above, any death that occurs after the follow up period of the study will not be reported to the sponsor.

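### Sections 9.5, 9.6 and 9.7 give inconsistent end dates for SAE and death reporting, and the 9.5 window can close before observation ends for a participant who withdraws from MBT only

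*Protocol*

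**What the plan says.** The protocol sets the end of safety reporting in four places.

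- **9.5, second paragraph (SAEs).** The window takes in "All SAEs occurring from the time of written informed consent until 6 months post cessation of trial treatment". Each such event goes on the CRF and reaches the sponsor within 24 hours of staff learning of it. By 9.1, death, life-threatening events and hospitalisation are all SAEs.
- **9.5, first paragraph (suicide).** Suicide-related SAEs are reported immediately, but "If a participant dies by suicide 6 months after the stud has ended, this will not be reported to the sponsor".
- **9.7 (deaths).** "All deaths will be reported to the sponsor irrespective of whether the death is related to disease progression" or to something else. The section then refers back to the preceding text as though the limit were the same, and states that "any death that occurs after the follow up period of the study will not be reported to the sponsor".
- **9.6 (chief investigator's duties).** All SAEs are to be recorded and reported within 24 hours. No end date is given.

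On how long participants are observed, 3.3 places the endpoint at 24 months: "This will include 18 months of treatment, and 6 months of follow up". For service use and self-harm, 3.7 has "Data to be taken from clinical records at 0,6,12,18, and 24 months". Section 7.7 allows withdrawal from MBT alone and adds: "Any participants that withdraw from the trial will be asked if they would like to continue to be involved in data collection, and follow up". The offer may be declined, and no end month is given for those who accept. Section 7.5 describes follow-up as the 6 months after the treatment phase. Section 7.9 ends the trial only when all participants have finished treatment and follow-up.

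**The concern.** There are two separate problems.

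First, staff who learn of a death have more than one rule to apply, and the rules disagree. A suicide after a participant's own follow-up but within 6 months of the study's end is reportable under one sentence of 9.5 and not under 9.7.

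Second, the SAE window is tied to the end of treatment, not to the end of observation. The two coincide for a completer. They need not coincide for someone who stops MBT and stays in data collection. A hospitalisation in that later period could be extracted from the record as a service-use outcome, yet 9.5 would not require an SAE form, and the form is where seriousness, causality and anticipation are recorded. With 10 to 14 participants, one event handled differently is visible in the safety summary.

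**Working it through.** **Inputs.** Treatment of 18 months and follow-up of 6 months (3.3); SAE window ending 6 months after treatment ceases (9.5); death limit at the end of follow-up (9.7); suicide limit at 6 months after study end (9.5); study end when the last participant finishes follow-up (7.9). Months are counted from the start of the 18-month treatment.

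**Plan's own figure.** 18 + 6 = 24 months, as 3.3 states.

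**Deaths, completer.**
- 9.5 SAE window: 18 + 6 = month 24.
- 9.7 death limit: end of follow-up = month 24.
- 9.5 suicide limit: study end + 6. The study cannot end before this participant's month 24, so the limit is at least 24 + 6 = month 30.
- Difference between the two death limits: at least 30 − 24 = 6 months, and more for anyone who finishes before the last participant.

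**SAEs, participant who withdraws from MBT only at month m.** On a per-participant reading the 9.5 window ends at m + 6. If the participant continues to month 24, the uncovered time is 24 − (m + 6) = 18 − m.

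| MBT stopped at month | 9.5 window ends | Observation after the window, to month 24 |
|---|---|---|
| 3 | 9 | 15 months |
| 6 | 12 | 12 months |
| 9 | 15 | 9 months |
| 12 | 18 | 6 months |
| 15 | 21 | 3 months |
| 18 | 24 | 0 months |

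**Alternative reading.** If follow-up for such a participant means the 6 months after their own treatment stopped, as 7.5 could be read, observation also ends at m + 6 and the gap is 0. The protocol does not say which applies, so the gap for a given stop month lies between 0 and 18 − m.

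**Which events are exposed.** Deaths fall under 9.7 until follow-up ends. Suicide-related SAEs fall under the first paragraph of 9.5, and 9.2 has life-threatening suicidal behaviour recorded throughout the study. What 9.5 leaves out is therefore non-fatal SAEs unrelated to suicide, mainly hospitalisations. Read literally, 9.6 would bring these back in, but it then contradicts the explicit window in 9.5.

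**The case against.** A reader might infer that treatment drop-outs remain under observation to month 24 and that their events go unreported. The protocol does not support that.

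- Continued data collection is an offer that can be declined, and month 24 comes from the general schedule, not from a rule for withdrawers.
- That the 9.5 window runs from each participant's own treatment end is the natural reading, but it is not spelled out.
- Deaths and suicide-related events are covered elsewhere, and 9.6 arguably covers the rest.
- The conflict over deaths is a separate matter. It concerns the time after follow-up, affects completers as well, and does not cause the drop-out gap. The back-reference in 9.7 suggests that a single limit was intended, so this may be a drafting slip.
- The stopping provisions in 7.7, 9.4 and 10.6 turn on a link to the study or intervention and are not confined to the 9.5 window. A missed stopping decision is therefore not shown.
- The allowance of 14 recruits for 10 completers does not imply 4 participants in the gap: 7.1 expects that loss in the screening and introductory phases. Nothing in the document says that those who stop therapy are the most likely to deteriorate.
- People who leave before the 18-month programme are a weak example. The flow chart puts the introductory group in the treatment phase while 8.1 describes treatment as 18 months, so their cessation date is unclear. However, a window without a closing date is not a gap, and section 4 ends data collection for those who leave the research entirely during baseline.

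All of this stands as a limit on the point. It does not remove it. An unlimited duty in 9.6 beside a limited one in 9.5 is itself an inconsistency. Six-monthly record extraction does not replace a 24-hour report with a causality judgement. Section 9.6 has adverse events checked when participants attend for treatment or follow-up, and someone who has stopped MBT no longer attends treatment.

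**Conclusion.** The point holds in limited form. Sections 9.5, 9.6 and 9.7 state end dates that cannot all apply, and for a completer the two death limits differ by at least 6 months. That part needs only the wording of those sections and the definition of study end in 7.9, taking the suicide sentence in 9.5 as a cut-off at 6 months after study end.

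The second part is conditional. It assumes that the 9.5 window is applied per participant, that the participant withdraws from MBT only and agrees to continue, and that continuation runs to month 24. The uncovered period is then 18 − m months and concerns non-fatal SAEs unrelated to suicide. The number of participants affected cannot be derived from the protocol. This should be corrected because it affects completeness of safety capture; it has no bearing on the power calculation or the efficacy analysis.

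**What to change.** Reconcile 9.5, 9.6 and 9.7 to one per-participant end date for all SAEs and deaths. That date should be no earlier than the participant's last data collection or record extraction, and no earlier than 6 months after the last MBT contact, with the introductory group counted as contact. Refer to the same date in 9.6, and state in 7.7 how long data collection continues for someone who withdraws from MBT only.

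The change should not cut coverage by accident: keep the longer reporting period for suicide now in 9.5 unless the sponsor deliberately alters it, and make 9.7 agree with it.

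The cost is a few sentences and possibly a few more SAE forms, for participants who are still under observation.

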9.6 Responsibilities

Chief Investigator (CI):

Checking for AEs and ARs when participants attend for treatment / follow-up.

- 1. Using judgement in assigning seriousness, causality and whether the event/reaction was anticipated
- 2. Using judgement in assigning seriousness and causality and providing an opinion on whether the event/reaction was anticipated
- 3. Ensuring that all SAEs are recorded and reported to the sponsor within 24 hours of becoming aware of the event and provide further follow-up information as soon as available. Ensuring that SAEs are chased with Sponsor if a record of receipt is not received within 2 working days of initial reporting.
- 4. Ensuring that AEs are recorded and reported to the sponsor in line with the requirements of the protocol.
- 5. Clinical oversight of the safety of patients participating in the trial, including an ongoing review of the risk / benefit.
- 6. Review of specific SAEs in accordance with the trial risk assessment and protocol as detailed in the Trial Monitoring Plan.
- 7. Preparing the clinical sections and final sign off of the Development Safety Update Report (DSUR).

Sponsor:

- 1. Central data collection and verification of AEs, SAEs according to the trial protocol onto a database.
- 2. Reporting safety information to the CI for the ongoing assessment of the risk according to the Trial Monitoring Plan.
- 3. Reporting safety information to the Trial Steering Committee (TSC)) according to the Trial Monitoring Plan.

Trial Steering Committee (TSC):

In accordance with the Trial Terms of Reference for the TSC, periodically reviewing safety data and liaising with the DMC regarding safety issues. This meeting reoccurs every 4 weeks, reducing to every 8 weeks once data collection has commenced.

In accordance with the Trial Terms of Reference, periodically reviewing overall safety data to determine patterns and trends of events, or to identify safety issues, which would not be apparent on an individual case basis.

9.7 Notification of deaths

All deaths will be reported to the sponsor irrespective of whether the death is related to disease progression, the IMP, or an unrelated event". As above, any death that occurs after the follow up period of the study will not be reported to the sponsor.

10 STATISTICS AND DATA ANALYSIS

10.1 Sample size calculation

We used an app that was designed to calculate power in multiple single case series studies (Single Case Designs (architecta.shinyapps.io/SingleCaseDesigns v3/). A permutation distance test, which is useful in this design because it corrects for auto-correlation, showed that with sample size of 10 and Cohen's d of 1 the power is close to 1. We are expecting some participants may drop out of the study, and so aim to recruit 14 potential participants.

10.2 Planned recruitment rate

The older adult MBT service in Manchester receives on average 2 applications of new patients per month and runs one group of MBT treatment of 8 patients. Each year, the service runs on average 2 introductory groups of 6 patients each. We are planning to start a second MBT treatment group in 2025. The sample size of 10-14 participants should be possible to achieve when the data collection of this study runs for a period of 3 years.

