7 TRIAL PROCEDURES

Process	Time
Community Mental Health Teams, and Therapy Hub Teams are notified of recruitment by poster, visits to team meetings, and email.	Prior to commencement of study
CMHT or Therapy Hub staff to discuss the trial with existing patients of the CMHT service. CMHT staff will gain consent for the trial team to contact the participant.	Prior to the commencement of study
Participant contacted by trial team. Brief information about trial provided. If participant is provisionally interested in joining the study, then they will be offered an initial appointment to be given the full participation information leaflet.	Prior to the commencement of study
Following the initial meeting, the participant will be given 7 days to decide if they want to be part of the trial.	0 days

After 7 days, the participant will be invited back to sign informed consent forms or withdraw from the study.	At 7 days
Participant contacted to advise them of the date of the introductory group.	At 1 months
Participants that complete the introductory group will become part of the baseline phase of the study.	At 4 months
Participants will have a baseline waiting period of 8 weeks. Outcome data will be collected during this phase. The participant will also start producing their MBT passport, and assessment collaboratively with a member of the treatment team.	At 8 months
Participants will begin MBT treatment for a period of 18 months. Outcome data taken weekly. Secondary outcomes and review of service use/self-harm taken every 6 months.	At 24-26 months
Follow up period will begin. Primary outcome data taken weekly.	Between 24-26 and 30-32 months
Qualitative interviews take place.	Between 30-34 months
Study end point. Data analysis and publication phase begins.	30-36 months
Dissemination of findings, publication.	Within 12 months following the last follow up data point of the final participant.

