10.8 Procedure(s) to account for missing or spurious data

The primary outcome data will be gathered weekly before each participant's individual MBT session, either by the therapist or via phone if the participant is absent. The secondary outcome measures will be collected by the research assistant. Patients will be attending at least weekly sessions at the location, so the research assistant and therapists will have regular contact with the participants to remind them to fill out the questionnaires.

In case of missing data we will try to find the reason that the participant did not fill out the questionnaire. In case of random missing data the data analysis contain an implicit imputation. In case of drop-out we will try to describe the reason for drop-out, because we are interested whether this treatment is feasible for older patients with personality disorders.

10.9 Other statistical considerations.

In case of slow recruitment rate an amendment to this protocol will be submitted to request for extension the recruitment period of 3 years.

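### Within a 3-year study the target of 14 cannot be recruited at the stated referral and group capacity, 10 needs near-full conversion, and the 3 years is defined in three ways

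*Protocol*

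**What the plan says.** **Size.** Section 7.1 wants data from 10 people and aims to recruit 14, expecting some attrition during screening and the introductory phase. Section 10.1 rests its power statement on 10 and gives 14 as the allowance for drop-out.

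**Supply.** According to Section 10.2 the service "receives on average 2 applications of new patients per month" and "Each year, the service runs on average 2 introductory groups of 6 patients each". It has one treatment group of 8, and a second is planned. The section concludes that 10-14 "should be possible to achieve when the data collection of this study runs for a period of 3 years".

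**Time per participant.** The Section 7 table counts from the information meeting (day 0). Its milestones are the introductory-group date at 1 month, completion of that group at 4 months, a row for the 8-week baseline marked 8 months, the end of treatment at 24-26 months, and follow-up "Between 24-26 and 30-32 months".

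**The 3 years.** Section 7.9 ends the trial only when everyone has finished treatment and follow-up, and adds: "The total length of the study may be up to 3 years". The Trial Summary gives 3 years as the planned trial period, and Section 7.7 requires an amendment beyond that. Section 10.2 attaches the same 3 years to data collection. Section 10.9 provides for an "extension the recruitment period of 3 years".

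**The concern.** A participant who needs 30-32 months uses most of a 36-month study, so the entry window is short. Section 10.2 offers its rates in support of 10-14 but does not subtract the time that each participant needs.

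Ten is the number behind the power statement and 14 is its margin for loss. Follow-up to 24 months belongs to the primary endpoint (Sections 3.3 and 3.4), so late entrants cannot simply be cut short. Recruitment rate is also one of the primary feasibility measures (Section 3.1). If the stated size and period do not fit together, an amendment can be foreseen at the outset, and a slow recruitment rate could not be told apart from a window that was too short.

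**Working it through.** **1. Time per participant, reproduced.** Following the table's intervals: 1 month to the group + 3 for the group + 2 of baseline + 18 of treatment + 6 of follow-up = 30 months. Taking the 8-month row as the start of treatment: 8 + 18 + 6 = 32. The stated 30-32 months therefore reproduces. The two ends differ only because 4 months plus 8 weeks is about 6 months, while the row says 8.

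**2. 3 years as the whole trial (Trial Summary, 7.7, 7.9).**
- Entry window: 36 − 32 = 4 to 36 − 30 = 6 months.
- Applicants at 2 a month: 8 to 12.
- For 14: 14/12 = 117% of applicants at best, so not reachable at the average rate.
- For 10: 10/12 = 83% of applicants in a 6-month window; 10/8 = 125% in a 4-month window.

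The protocol gives no rate at which applicants become participants, so the table shows a range of assumed rates.

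| Assumed conversion | Entry time for 10 | Total for 10 (months) | Entry time for 14 | Total for 14 (months) |
|---|---|---|---|---|
| 100% | 5.0 | 35-37 | 7.0 | 37-39 |
| 75% | 6.7 | 36.7-38.7 | 9.3 | 39.3-41.3 |
| 50% | 10.0 | 40-42 | 14.0 | 44-46 |

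**3. Introductory groups on the same reading.** Everyone passes through one before baseline. Two a year, evenly spaced (an assumption; the protocol says only that two is the average), with the first at month 1, gives:

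| Group | Starts (month) | Cumulative places | Follow-up ends (month) |
|---|---|---|---|
| 1 | 1 | 6 | 30-32 |
| 2 | 7 | 12 | 36-38 |
| 3 | 13 | 18 | 42-44 |

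Fourteen needs a third group. Ten needs 10/12 = 83% of the places in two groups, with the second finishing no earlier than month 36. Twelve is a ceiling, because the flow chart and Section 7.1.2 let people who decline the research or miss the diagnostic criterion still receive MBT.

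**4. 3 years as data collection (10.2).** The flow chart starts weekly data collection at baseline, so each participant contributes 8 weeks + 18 + 6 = about 25.8 months. The entry window is 36 − 25.8 = about 10.2 months, with about 20 applicants. Counted from the first group's baseline, group 2 ends at 6 + 25.8 = 31.8 months and group 3 at 12 + 25.8 = 37.8 months. So 10-12 fits, and 14 does not at average spacing.

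**5. 3 years as recruitment (10.9).** There would be 2 × 36 = 72 applicants and 12 × 3 = 36 introductory places, so 10-14 is easy. The last participant would finish at 36 + 30 = 66 to 36 + 32 = 68 months, against a total of up to 36.

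**The case against.** **The ranges overlap.** A reader might infer that 10-14 cannot be reached at all. The figures do not support that: 8-12 applicants and up to 12 places both include 10. Ten is tight, not impossible.

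**Averages are not ceilings.** This stands. If applications were Poisson at 2 a month (an assumption), the chance of at least 14 would be about 32% in 6 months and 3% in 4 months, before any loss. Section 7 also has teams approaching existing patients before the study starts, which could supply a waiting pool. That eases the referral limit but not the introductory places. The second treatment group adds treatment places, not introductory ones.

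**Group spacing is assumed.** This also stands. Even on the slower clock, a second group that started by month 5 would finish at 5 + 31 = 36. The figure of 42-44 months likewise depends on even spacing.

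**Section 10.2 speaks of data collection.** On its own words 10-12 is achievable. That narrows the point, but 14 still does not fit at average spacing, and the section then conflicts with Section 7.9.

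**Further inferences to avoid.** A reader might multiply places by 10/14 to predict completers. Section 7.1 puts that loss partly in screening, which comes before a place is filled, so the product would count it twice. A reader might expect follow-up to be truncated, but Section 7.9 requires full follow-up, and Sections 7.7 and 10.9 provide for amendments. Nor can one say that recruitment will be judged against an impossible target, because the table of feasibility aims is not in the document.

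**Conclusion.** The stated size and period are inconsistent. If the trial lasts 3 years in total, the entry window is 4-6 months and the supply is 8-12 applicants and at most 12 introductory places. The target of 14 is then not reachable at the stated average rates, and 10 requires at least 83% conversion on the faster clock. Reading the 3 years as data collection allows 10-12 but not 14. Reading it as recruitment allows 14 easily but lengthens the study to about 66-68 months.

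The result rests on the Section 7 durations, on the average rates in Section 10.2, and, for the group-based figures, on even six-month spacing. The protocol already has an amendment route for overrun, so what needs correcting is the stated plan. No loss of data is shown to be likely.

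**What to change.** 1. Define the 3 years once, and make the Trial Summary and Sections 7.7, 7.9, 10.2 and 10.9 agree.
2. Reconcile the 8-month row in Section 7 with completion of the introductory group at 4 months plus an 8-week baseline, or explain the gap.
3. Then choose one of two courses:
   - Restate the planned period so that 14 fits. That is about 42-44 months if three evenly spaced introductory groups are needed. State a last-consent date; on that spacing the last information meeting falls at about month 12, since 12 + 30 = 42 and 12 + 32 = 44.
   - Keep 36 months and restate the recruitable sample as at most about 12, with entry closing at month 4-6 according to how step 2 is settled.
4. In Section 10.2, show the expected conversion from applicant to participant and the planned group start dates, so that the claim can be checked.

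The cost is one amendment to dates or to the stated size. No extra patients or assessments are needed; the stated timeline becomes longer or the stated sample smaller.
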